3.1.5 Data Presentations

All data will be summarized by dose level. For each study, a separate study-specific total should summarize all dose levels for that study. In addition, an overall column that includes all participants of both studies should also be presented.

The following table summarizes the number of dosed participants and the associated dose levels in studies MGT006 and MGT012.

Dose Level (vg/mL)	Number of MGT006 Participants Dosed	Number of MGT012 Participants Dosed
	3	3
	12	3
	3	NA
	5	5
Study Total	23	11

Unscheduled measurements and repeat measurements not due to technical failure will be listed but not summarized. If a repeat measurement is due to a technical failure, it will be included in the summaries.

3.2 Analysis Populations

3.2.1 Safety Analysis Set (SAF)

The Safety Analysis Set (SAF) consists of all enrolled participants who have been administered vector in the parent study (MGT006 or MGT012).

3.2.2 Full Analysis Set (FAS)

The Full Analysis Set (FAS) includes all enrolled participants who were diagnosed with CNGA3- or CNGB3-related achromatopsia, who were administered vector, and who had at least one post-baseline assessment for efficacy. Participants will be presented according to the dose level they received.

Study completion/withdrawal and protocol deviations will be summarized using the FAS set. Background and demographic characteristics will be summarized using the SAF. The primary and secondary efficacy endpoints will be summarized using the FAS. Prior/concomitant medications, administration of study treatment, and exposure and safety will be summarized using the SAF.

3.3 Subject Data and Study Conduct

3.3.1 Subject Disposition

Subject disposition will include the number and percentage of (1) all participants enrolled, (2) participants included in the safety analysis set, (3) participants in the full analysis set, (4) participants who completed the study, and (5) participants who prematurely discontinued follow-up. The number and percentage of participants will be summarized by their reasons for withdrawal from follow-up. Individual reasons for withdrawal will be presented in a listing.

Eligibility for each of the analysis sets, along with reasons for exclusion, will be listed. Study completion/withdrawal data will be listed.

3.3.2 Protocol Deviations

Counts and percentages of subjects with protocol deviations by deviation category will be summarized by treatment and in total based on all enrolled subjects. Major deviations will be summarized separately.

3.3.3 Demographic and Baseline Characteristics

Demographic characteristics (age, sex, ethnic origin, race, country, and adult or pediatric) and body measurements (height, weight, and body mass index (BMI)) will be carried over from the respective parent studies.

All participant demographic data, including informed consent, will be listed.

3.3.4 Concomitant Medications

Medications will be coded using the latest World Health Organization (WHO) Drug Dictionary version, which will be indicated in the data summaries and listings.

Medications that are ongoing at the time of MGT007 study enrollment will be deemed to be concomitant medications. If medication dates are incomplete and it is not clear whether the medication was concomitant, it will be assumed to be concomitant.

The number and percentage of participants taking concomitant medications will be summarized by medication class and standardized medication name, where medication class and standardized medication name will be presented in decreasing frequency of the total number of participants with medications. In summary tables, participants taking multiple medications in the same medication class or having the same standardized medication recorded multiple times in the study will be counted only once for that specific medication class and standardized medication name.

Medication data will be listed, and concomitant medications will be flagged.

3.4 Safety Evaluation

3.4.1 Adverse Events

AE will be coded using the latest MedDRA dictionary version. The version used will be indicated in the data summaries and listings.

A TEAE is defined as an AE that started on or after the start of the administration of ATIMP. If adverse event dates are incomplete and it is not clear whether the adverse event was treatment-emergent, it will be assumed to be treatment-emergent.

A treatment-related TEAE is defined as a TEAE that is possibly, probably, or definitely related to ATIMP or ATIMP surgery. If the TEAE has a missing relationship it is assumed to be related to ATIMP for analysis purposes.

A summary table will present the following by dose group in the dose escalation and dose expansion phase:

- TEAEs (events and participants).
- Serious TEAEs (events and participants).
- Serious study treatment-related TEAEs (events and participants).
- TEAEs by severity (CTCAE grade version 4.0) (events and participants).
- TEAEs by relationship to ATIMP and the pooled ATIMP-related [possibly, probably, and related] category (events and participants).
- TEAEs by relationship to ATIMP surgery and the pooled ATIMP-related [possibly, probably, and related] category (events and participants).
- TEAEs leading to withdrawal from study (participants only).
- TEAEs leading to death (participants only).

If a participant experienced more than one TEAE, the participant will be counted once using the most related event for the "by relationship to study treatment" and "related to study treatment" summaries and at the worst severity for the "by severity" summary.

The following tables will be presented:

- TEAEs by SOC and PT.
- TEAEs by SOC, PT, and severity (CTCAE grade version 4.0).
- TEAEs by SOC, PT, and relationship to ATIMP and the pooled related categories (related [possibly, probably, and related]).
- TEAEs by SOC, PT, and relationship to ATIMP surgery and the pooled related categories (related [possibly, probably, and related]).

For all of the above, SOC and PT will be presented in decreasing frequency of the total number of participants with TEAEs.

Further details of the above five tables are given below:

- If a participant experienced more than one TEAE the participant will be counted once for each SOC and once for each PT
- If a participant experienced more than one TEAE the participant will be counted once for each PT.
- If a participant experienced more than one TEAE the participant will be counted once for each SOC and once for each PT at the worst severity.
- If a participant experienced more than one TEAE the participant will be counted once for each SOC and once for each PT using the most related event.

Adverse event data will be listed in full, and this will also include a treatment-emergent flag, the time of onset and cessation of event relative to first administration of ATIMP and duration of AE.

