2.2 Study Design

2.2.1 Overview

Participants will be invited to provide consent for this longer-term follow-up study during the CNGB3 (MGT006) trial or CNGA3 (MGT012) trial. During this longer-term follow-up study participants will be assessed for safety for up to 60 months following AAV8-hCARp.hCNGB3 or AAV8-hG1.7p.coCNGA3 administration in study MGT006 or study MGT012.

The duration of long-term follow-up is therefore consistent with the recommendations of the current CHMP Guideline on Follow-up of Patients Administered with Gene Therapy Medicinal Products (EMEA/CHMP/GTWP/60436/2007) of 22 October 2009, where it is stated that, for viral vectors without integration, latency or reactivation potential, a brief clinical history and sample testing should be performed pre-treatment, at 3, 6 and 12 months after treatment, and then yearly thereafter for a minimum of 5 years (and, if non-clinical tests or evidence from other clinical trials using identical vectors or modifications of vectors indicate a potential for integration or late re-activation, the monitoring should be extended to continue yearly after those 5 years until data indicate that there is no longer any risk to be followed). Further, although the Food and Drug Administration (FDA) Guidance for Industry: Gene Therapy Clinical Trials – Observing Subjects for Delayed Adverse Events (November 2006) recommends a standard 15-year period of follow-up, it is also noted that a shorter period of follow-up may be possible if the vector does not integrate and has no potential for latency and reactivation. The follow-up study will be a non-intervention study designed to collect data on longer-term safety and efficacy at the equivalent of 9, 12, 18, 24, 36, 48, and 60 months following ATIMP administration.

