2.2.3 Sample Size Determination

This is a long-term follow-up study; therefore, there is no formal sample size calculation.

23 and 11 participants were randomized and dosed in the MGT006 and MGT012 studies, respectively. All participants enrolled in the MGT006 and MGT012 studies were invited to participate in this follow-up study.

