3.1.4 Summary Statistics

Categorical data will generally be summarized with counts and percentages of subjects. The denominator used for the percentage calculation will be clearly defined. Continuous data will generally be summarized with descriptive statistics including n (number of non-missing values), mean, median, standard deviation, Q1, Q3, minimum, and maximum.

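### The planned adverse-event summaries take no account of follow-up time, so if participants leave early the crude percentages understate 5-year risk, most of all for late harms

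*SAP*

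**What the plan says.** The primary objective is longer-term safety (Protocol 4.5.1; SAP 2.1.1), with follow-up for up to 60 months after dosing. SAP 2.2.1 supports that duration partly by citing FDA guidance titled in part "Observing Subjects for Delayed Adverse Events".

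- **Adverse-event tables.** SAP 3.4.1 counts a treatment-emergent event from vector administration onwards. The overview table starts with "TEAEs (events and participants" and continues in the same form for serious, related and graded events. The remaining tables are by system organ class and preferred term.
- **Summary measure.** SAP 3.1.4: "Categorical data will generally be summarized with counts and percentages of subjects". It adds: "The denominator used for the percentage calculation will be clearly defined".
- **Population.** SAP 3.2.1: "The Safety Analysis Set (SAF) consists of all enrolled participants who have been administered vector in the parent study (MGT006 or MGT012"). No length of follow-up is required. SAP 3.2.2 states that "administration of study treatment, and exposure and safety will be summarized using the SAF", but no exposure or follow-up-time summary is defined anywhere.
- **Leavers.** SAP 3.3.1 tabulates "participants who prematurely discontinued follow-up", summarises the reasons and lists them individually. Protocol 5.6.1 keeps the data already collected and gives no censoring or person-time rule.
- **Listings.** SAP 3.4.1 lists every adverse event with its onset and end relative to dosing, and its duration.

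**The concern.** On the safety-set denominator, a participant last seen event-free at Month 12 adds the same to a percentage as one seen event-free at Month 60. The tables also put events around surgery and events in year 5 into one count. The purpose of the study is to learn what happens late, and late events are the ones most likely to be missed when someone leaves.

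Two conclusions are at stake. One is the size of any late risk. The other is how much reassurance an absence of late events gives, which depends on how many participants were still being watched. Dose levels hold 3, 5 or 12 participants, so one early leaver can remove a third of the late observation in a column without any sign of it in the adverse-event table.

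**Working it through.** **Inputs from the documents.** SAP 2.2.3: "23 and 11 participants were randomized and dosed in the MGT006 and MGT012 studies, respectively". The dose-level rows in SAP 3.1.5 reproduce this: 3 + 12 + 3 + 5 = 23 and 3 + 3 + 5 = 11, total 34. The first visit in this study is at Month 9 and the last at Month 60 (Protocol 5.6).

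**Assumed, because the documents give no figure.** A fraction d of 10, 20 or 30% leaves, at times spread evenly over Months 9 to 60 and unrelated to risk. The true 5-year risk F(60) is 30%. The denominator is the whole safety set.

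**Formula.** Expected crude risk = (1 − d) × F(60) + d × M, where M is the average of F(t) over t from 9 to 60 months.

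*Constant hazard.* λ = −ln(0.70)/60 = 0.00594 per month. M = 1 − (e^(−9λ) − e^(−60λ))/(51λ) = 1 − (0.9479 − 0.7000)/0.3032 = 0.1823.

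*Events only in Months 36 to 60, evenly spread.* F(t) = 0.30 × (t − 36)/24 in that period and 0 before it. M = (0.30 × 24/2)/51 = 0.0706.

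| Dropout d | Constant hazard | Events in Months 36–60 only |
|---|---|---|
| 0% | 30.0% | 30.0% |
| 10% | 0.9 × 0.30 + 0.1 × 0.1823 = 28.8% | 0.9 × 0.30 + 0.1 × 0.0706 = 27.7% |
| 20% | 27.6% | 25.4% |
| 30% | 26.5% | 23.1% |

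The extreme, with every leaver gone before any event occurs, is 0.30 × (1 − d) = 27, 24 and 21%. That is a bound and not an expectation.

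**In participants.** At a true 30%, the shortfall under a constant hazard is 0.3 to 0.8 of 23 and 0.1 to 0.4 of 11. For late events only it is 0.5 to 1.6 of 23 and 0.3 to 0.8 of 11.

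**Sensitivity to the dropout model.** Take exponential dropout with hazard m and event hazard l. For risk accruing over Months 9 to 60 (T = 4.25 years) the crude figure is l/(l + m) × [1 − e^(−(l+m)T)]. For risk in Months 36 to 60 only it is e^(−2.25m) × l/(l + m) × [1 − e^(−2(l+m))]. At a true 30% and 10 to 30% dropout these give 28.6 to 25.5% and 27.7 to 23.0%. The direction and rough size are the same, and the relative shortfall hardly changes for true risks of 10 or 20%.

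**No late events seen.** The exact one-sided 95% upper limit is 1 − 0.05^(1/n). It is 8.4% if all 34 are followed to Month 60 and 11.7% if 24 are (24 is illustrative, and pooling the products is for illustration only). For one product with full follow-up it is 12.2% for 23 and 23.8% for 11. The planned adverse-event tables would look the same with 34 or 24 participants still under observation.

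**The case against.** A reader might infer that the SAP counts leavers as free of events for five years and that late harms are therefore understated. The documents do not support that as a statement of fact.

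- No section defines a 60-month adverse-event risk. The counts are valid as counts of observed events, and anyone with an event before leaving is still counted. The shortfall arises only when the percentage is read as a 5-year risk.
- The shortfall needs dropout. The documents quantify none. Protocol 5.6.2 expects participants to stay committed, and 5.6.1 asks that those who withdraw still be followed if willing. A discontinuation row in SAP 3.3.1 is routine and predicts nothing.
- The safety-set denominator is an inference from SAP 3.2.2. SAP 3.1.4 leaves the denominator to be defined.
- Onset times and withdrawals are listed. With at most 34 people, a careful reader can reconstruct who was watched and for how long.
- The shortfall is small beside the sampling error. Exact 95% intervals are about 13 to 53% for 7/23 and 6 to 61% for 3/11.
- A Kaplan-Meier curve from dosing is not a simple addition. The first visit is at about Month 9 (Protocol 5.3.4), and initial consent may come at Month 3, Month 6 or later (Protocol 5.6, footnote 1). If parent-study events are left out, entry is delayed and must be handled. Any censored estimate also assumes that leaving is unrelated to risk.

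All of this stands, and it makes the point conditional. It does not close the gap: a listing is not a summary, and a primary safety conclusion should not rest on reconstruction by hand.

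**Conclusion.** The point holds in conditional form. Every aggregate adverse-event output is a count or a crude percentage, with no follow-up time, number under observation or split by time since dosing. With complete follow-up there is no bias.

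If the assumed 10 to 30% leave over Months 9 to 60, a true 30% risk would show about 1 to 4 percentage points low under a constant hazard, and about 2 to 7 points low if harms come only in Months 36 to 60. These sizes rest on assumed dropout, assumed risk, uninformative leaving and the full safety set as denominator. This is a cheap improvement to a descriptive plan, not the correction of a wrong analysis.

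**What to change.** In SAP 3.4.1 add, by product and descriptively, for treatment-related and serious treatment-emergent events:

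1. Participant-years of follow-up and the number under observation at each scheduled visit, also by dose level. This defines the exposure summary named in SAP 3.2.2 and lets a reader judge the dose columns.
2. Adverse events by time since dosing, for example to Month 12, Months 12 to 36 and Months 36 to 60, with events per participant-year.
3. Cumulative incidence censored at last contact. State whether parent-study events are included. If they are not, count time at risk from entry to MGT007 (delayed entry).

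Report the 15-letter loss in SAP 2.3.1 by scheduled visit, with the number assessed as denominator, because acuity is measured only at visits.

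The crude tables can stay. Onset relative to dosing is already derived for the listing, so the cost is one or two more tables. Estimates will be imprecise with at most 23 and 11 participants. Cumulative incidence by dose level is not worth attempting in groups of 3 to 12.

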3.4.2 Clinical Laboratory Evaluation

No current plans to analyze the sample collected in study MGT007 for immunological response.

3.4.3 Pregnancy Test

All pregnancy data will be listed.

3.5 Efficacy Evaluation

3.5.1 Test-Retest

The test-retest values from studies MGT006 and MGT012 will be used for the MGT007 final analyses.

The protocol describes efficacy as being indicated by:

Any improvement in visual function from baseline that is greater than the test-retest variation for that test and is sustained for at least 2 consecutive assessments.

Participants who have a post baseline reading greater than the test-retest value for at least 2 consecutive assessments will be classed as a visual function improvement for the relevant test.

The test-retest variation for each visual function assessment will be calculated for each participant who has at least one set of test-retest data as:

$$Test - retest = 1.96 \sqrt{S_p^2}$$

where S_p^2 is the within-participant variance for each participant and will be derived as:

$$\frac{(n1-1)\sum_{(yi1-ybar1)}2+(n2-1)\sum_{(yi2-ybar2)}2}{n1+n2-g}$$

Where:

yi1 is the ith baseline observation in the left eye
ybar1 is the mean of baseline observations in the left eye
yi2 is the ith baseline observation in the right eye
ybar2 is the mean of baseline observations in the right eye
n1= number of baseline observations in the left eye
n2= number of baseline observations in the right eye
g is the number of eyes =2

The test-retest variation for each visual function assessment of the difference between the study eye and fellow eye will also be calculated for each participant who has at least one set of test-retest data using the same formula except S_n^2 will be derived as

$$\frac{\sum_{(yi-ybar)}2}{n-g}$$

Where:

yi is the ith baseline observation in the difference of the study eye and fellow eye ybar is the mean of baseline observations in the difference of the study eye and fellow eye n= number of baseline observations in the difference of the study eye and fellow eye (vary from 2 to 3) g is 1

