#### 5.9.3.2 Statistical Methods - Secondary Outcome Analysis

The secondary outcomes are measures of the efficacy of each ATIMP; these will be performed on an individual participant basis and will be primarily descriptive in nature. Standard assessments will be used to measure visual function and established methods of analysis, appropriate for the assessment will be used to evaluate the data. For specialist assessments, data will be analysed by the expert team member(s) who developed the assessment. Final data will be reported descriptively.

Efficacy will be indicated by:

- 1) Any improvement in visual function from baseline that is greater that the test-retest variation for that test and is sustained for at least 2 consecutive assessments.
- 2) Any improvement in retinal function from baseline that is greater than test-retest variation and measurable by electrophysiology (pattern ERG, or full-field ERG).

Measures will be reported individually and aggregated across participants as the proportion who satisfy the above criteria.

Quality of life patient reported outcome measures will be used to correlate a participant's feeling about their own wellbeing with clinical observations.

Any deviations from the original statistical plan will be described in the final report, as appropriate.

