2.3.2 Secondary Endpoints

The secondary outcomes are measures of the efficacy of the ATIMP; these will be performed on an individual participant basis and will be descriptive in nature:

- 1) Any improvements in visual function from baseline that are greater than the test-retest variation and are sustained for at least two consecutive assessments.
- 2) Any improvement in retinal function from baseline that is greater than test-retest variation and measurable by electrophysiology (pattern ERG, or full-field ERG).
- Quality of life will be measured by the Impact of Visual Impairment (IVI) questionnaire and the EQ5D-5L.

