3.5.2 Visual Acuity

Visual acuity was assessed at the Month 9, 12, 18, 24, 36, 48, and 60 visits.

4 meter refraction of the sphere, cylinder, and axis of each eye will be measured. Best-corrected ETDRS visual acuity will be measured.

The arithmetic mean of the multiple observations at baseline will be used as the baseline value.

Achievement of visual improvement above the test-retest variation (yes/no) as measured by a number of ETDRS letters will be summarized for study eye and the difference between eyes (study eye minus fellow eye) for all participants.

The 4-meter refraction (sphere, cylinder, and axis) observed values will be summarized for the study eye for all participants.

Summary statistics of all ETDRS visual acuity observed values and the change from baseline by study eye and the difference between eyes (study eye minus fellow eye) for all participants will be presented.

The difference between the study eye and the fellow eye of ETDRS letters, the difference at each visit, along with its change from baseline data, will be summarized. At each post-baseline visit, the change from baseline in the difference between the study eye and the fellow eye will be tested by a nonparametric Wilcoxon signed rank test as the primary method. The p-value from the t-test and the Shapiro-Wilk Normality test will also be provided.

All visual acuity data will be listed.

In-text displays:

- Average Plot of BCVA (ETDRS Letters) Change from Baseline Over Time
- Individual Plot of BCVA (ETDRS Letters) Change from Baseline Over Time

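### The SAP 3.5.1 responder rule compares the post-baseline reading, not the change from baseline, with the test-retest value, which contradicts the stated criterion

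*SAP*

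**What the plan says.** The criterion appears in the same form in several places. SAP 2.3.2 gives the first secondary endpoint as "Any improvements in visual function from baseline that are greater than the test-retest variation and are sustained for at least two consecutive assessments". Protocol 5.5.2 agrees, and protocol 5.9.3.2 repeats it and adds that results will be aggregated as the proportion of participants who meet it. SAP 3.5.1 restates it, counting consecutive assessments: "Any improvement in visual function from baseline that is greater than the test-retest variation for that test and is sustained for at least 2 consecutive".

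The next sentence of SAP 3.5.1 turns the criterion into a classification. The group it counts as improved on a given test is "Participants who have a post baseline reading greater than the test-retest value for at least 2 consecutive assessments". It mentions neither baseline nor change.

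The test-retest value is 1.96 times a within-participant standard deviation calculated from the repeat baseline readings. SAP 3.5.2 defines a baseline value ("The arithmetic mean of the multiple observations at baseline will be used as the baseline value") but does not link it to the classification. It then says "Achievement of visual improvement above the test-retest variation (yes/no) as measured by a number of ETDRS letters will be summarized for study eye", with the same summary for the between-eye difference. SAP 3.5.3 and 3.5.4 follow the same pattern for contrast sensitivity and maximum reading speed. SAP section 4, which lists changes from the protocol analysis, does not mention the rule.

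**The concern.** A test-retest value is on the scale of a difference: a few letters, a fraction of a LogCS unit, some words per minute. A reading is the participant's whole score. Comparing the two asks whether the participant can see appreciably more than nothing, not whether vision has improved. For the between-eye difference the slip is harder to notice, because those values lie nearer zero.

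The sentence governs the yes/no result for all three visual-function tests that the SAP still analyses, in both its study-eye and between-eye forms. SAP section 4 withdraws full-field and pattern ERG from analysis, so the second secondary endpoint cannot be evaluated. The responder proportions are then the only efficacy results judged against a stated criterion, in at most 23 + 11 = 34 dosed participants with no control group.

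**Working it through.** The documents give no expected responder rate, so there is no figure to reproduce. The check applies the rule to worked examples and then to simulated participants with no true change.

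**From the SAP.** Bar = 1.96 × √S². For the study eye, S² = [(n1−1)·SS1 + (n2−1)·SS2] / (n1 + n2 − 2), where SS is the sum of squared deviations of one eye's baseline readings. For the between-eye difference, S² = SS/(n − 1). SAP 3.5.1 gives 2 to 3 baseline observations of the difference. There are seven post-baseline visits (Months 9 to 60).

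**Assumed.** All score levels and SDs, because the documents give none.

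**Study-eye example.** Both eyes read 38, 40 and 42 at baseline.
- SS = 4 + 0 + 4 = 8 per eye.
- S² = (2×8 + 2×8)/4 = 8, so the bar is 1.96 × √8 = 5.5 letters.
- Follow-up readings of 40 and 40 both exceed 5.5, so the participant is classed as improved. The change is 0.
- Readings of 20 and 20, a loss of 20 letters, also pass.
- With noisier baselines of 35, 40 and 45, SS = 50, S² = 50 and the bar is 13.9 letters. A reading of 40 still passes.

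**Between-eye examples.**
- Baseline differences 8, 10, 12: S² = 8/2 = 4, bar = 1.96 × 2 = 3.9. Follow-up differences of 10 pass although the change is 0.
- Baseline differences −12, −10, −8: same bar. If the study eye gains 10 letters, the follow-up difference is 0, which fails, although the change of +10 is well above the bar.

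**Simulation.** 40,000 participants, no true change, independent normal error, seven visits, a participant-specific bar from the printed formulas, responder = above the bar at two consecutive visits.

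Study eye, true score 35 letters, within-eye SD 3:

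| Baseline readings per eye | Reading vs bar (as written) | Change vs bar |
|---|---|---|
| 2 | about 100% | 14% |
| 3 | about 100% | 3% |

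The printed formula multiplies each SS by (n−1). With ordinary pooling and three readings the change-based figure is about 8%; with two readings the formulas coincide. With three readings and a true fall to half the score (17.5 letters), the literal rule still classes over 99% as improved at SD 3 and about 87% at SD 5.

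The result is similar for all three tests under other assumed values (40 letters, SD 3 to 5; LogCS 1.0, SD 0.10 to 0.15; 90 words per minute, SD 10 to 15; between-participant SDs 8, 0.2 and 25). As written, 97% to 100% are responders; using change, about 3% (three readings) or 14% (two).

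Between-eye difference, within-eye SD 3, constant study-eye advantage, no change:

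| Advantage (letters) | As written, 3 readings | As written, 2 readings |
|---|---|---|
| −10 | about 0% | about 0% |
| 0 | 9% | 18% |
| 5 | 46% | 55% |
| 10 | 82% | 82% |

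Using change, the figure is about 13% (three readings) or 21% (two), whatever the advantage.

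**The case against.** The strongest reply is that this is a slip of wording. The preceding sentence, SAP 2.3.2 and two protocol sections all say from baseline; the disputed sentence itself speaks of improvement; and no sensible programmer would call an unchanged score an improvement. Detailed programming specifications are in a separate document (SAP section 5) that is not available here. This stands as far as intent goes. A reader might infer that the reported study-eye proportion will be close to 100%; the documents do not show that the literal rule will be programmed. But the SAP then holds two incompatible definitions, and correct programming would depart from its only operative one.

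A second reply is that little depends on it. The secondary outcomes are descriptive, the primary endpoint is safety, and the Wilcoxon and t-tests already use change from baseline in the between-eye difference. Change summaries and plots would expose an implausible responder table. This also stands: it limits the consequence but does not make the rule correct.

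A third point is direction. It is tempting to say that the literal rule always inflates the responder proportion. That holds for study-eye scores well above the bar. It fails for a participant scoring near zero, and for the between-eye difference when the eyes start equal (9% as written against 13%) or the study eye starts worse. The documents give no baseline asymmetry, so the size and sign of the between-eye error are unknown.

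**Conclusion.** The point holds as a contradiction within the SAP. The operative sentence in 3.5.1 does not implement the endpoint that the protocol and SAP define, and nothing elsewhere in the SAP corrects it. Applied literally, it makes the study-eye proportion uninformative: about 100% of unchanged participants respond, against 3% or 14% when change is used with the printed formula and three or two baseline readings. The between-eye proportion becomes largely a function of pre-treatment asymmetry, too high or too low by an amount that the documents do not allow one to estimate.

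The percentages rest on assumed score levels, error SDs and normal independent errors. The study-eye conclusion needs only that an unchanged score exceeds the bar. The finding concerns a descriptive secondary endpoint. It does not touch the primary safety endpoint and is not evidence that the analysis has been or will be programmed wrongly.

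**What to change.** Replace the classification sentence in SAP 3.5.1 with:

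> A participant whose change from baseline (post-baseline value minus the mean baseline value) exceeds the test-retest value at two or more consecutive assessments will be classed as having a visual function improvement for that test. For the between-eye endpoint the rule applies to the change from baseline in the difference (study eye minus fellow eye).

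Check that the programming specifications agree. SAP section 1 says that the SAP is finalised before database lock, so the correction belongs before that point.

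The cost is one sentence and no new data. The study-eye proportion will be lower than under the literal rule; the between-eye proportion may go up or down. Some unchanged participants will still be classed as responders (in the simulation, 3% to 14% for the study eye and 13% to 21% between eyes), because each bar is estimated from two or three baseline readings and seven visits give several chances to pass it. The report should say so beside the proportions.
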